## 6.1.1.2. Systemic Events

Results from systemic events after each dose (Dose 1, Dose 2, Dose 3, and Dose 4) will be summarized separately.

## 6.1.1.2.1. Main Analysis

- Estimand: The percentage of participants reporting prompted systemic events (fever, decreased appetite, irritability, and drowsiness/increased sleep) within 7 days after each dose (Section 2.1).
- Analysis set: Safety population (Section 4).
- Analysis time point: Within 7 days after each dose.
- Analysis methodology: The between-group difference (20vPnC 13vPnC) and the corresponding 2-sided 95% CI will be calculated using the Miettinen and Nurminen method (Section 5.2.1) for each event.

Intercurrent events and missing data: Missing values will not be imputed. CCI •

Reporting results: Count and percentage of participants with the indicated endpoint and the associated 2-sided 95% CI for each and any systemic event after each dose in each vaccine group will be presented by maximum severity across severity levels. Between-group differences (20vPnC – 13vPnC) in these percentages and their 2-sided 95% CIs will also be provided.

6.1.1.3. Adverse Events

- 6.1.1.3.1. Main Analysis
- Estimands: •

CCI

- The percentages of participants reporting AEs from Dose 1 through 1 month after • Dose 3 (Section 2.1).
- The percentages of participants reporting AEs from Dose 4 through 1 month after • Dose 4 (Section 2.1).

- Analysis set: Safety population (Section 4).
- Analysis time points: Dose 1 through 1 month after Dose 3, Dose 4 through 1 month after Dose 4.
- Analysis methodology: 3-Tiered approach as described in Section 5.2.1. •
- Intercurrent events and missing data: No missing values will be imputed except for partial AE start dates (Section 5.3).
- Reporting results: For all 3 tiers, the numerator (n) and the denominator (N) used in the • percentage calculation, the percentage (%), and the corresponding 2-sided 95% CI for participants reporting any AE, each system organ class, and each preferred term within system organ class will be presented by vaccine group.

In addition, for AEs classified as Tier 2 events, the differences in percentages (20vPnC - 13vPnC) and associated 2-sided 95% CIs will be provided.

Further, for Tier 1 events, if any are identified, the difference in percentages, the associated 2-sided 95% CI for the risk difference, and the asymptotic p-values will also be provided.

CCI

# 6.1.1.4. Serious Adverse Events and Newly Diagnosed Chronic Medical Conditions

#### 6.1.1.4.1. Main Analyses

- Estimands:
  - The percentage of participants reporting SAEs from Dose 1 through 6 months after Dose 4 (Section 2.1).
  - The percentage of participants reporting NDCMCs from Dose 1 through 6 months after Dose 4 (Section 2.1).
- Analysis set: Safety population (Section 4).
- Analysis time point: Dose 1 through 6 months after Dose 4.
- Analysis methodology: Descriptive summary statistics.
- Intercurrent events and missing data: No missing values will be imputed except for partial SAE/NDCMC start dates (see Section 5.3).
- Reporting results: The numerator (n) and the denominator (N) used in the percentage calculation, the percentage (%), and the corresponding 2-sided 95% CI for participants reporting any SAEs/NDCMCs, each system organ class, and each preferred term within system organ class will be presented by vaccine group. SAEs and NDCMCs will be presented separately. There will be a listing of all AEs, including SAEs and NDCMCs, and a separate listing of SAEs only.

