# 2.1. Study Objectives, Endpoints, and Estimands

The estimands corresponding to each primary CCI objective are described in Table 2. The estimands to evaluate the safety objectives are based on the safety population (see Section 4 for definition). These estimands estimate the safety profile of 20vPnC from participants in the study who receive at least 1 dose of 20vPnC with safety data.

In the safety objective evaluations, missing AE start dates will be imputed according to Pfizer safety rules (Section 5.3). No other missing information will be imputed in the safety analysis.

Primary Safety Objective	Primary Safety Estimands	Primary Safety Endpoints
• To describe the safety profile of 20vPnC	
 
In participants receiving at least 1 dose of investigational product with safety follow-up after any vaccination:
 
The percentage of participants reporting prompted local reactions within 7 days after each vaccination in each group
 
The percentage of participants reporting prompted systemic events within 7 days after each vaccination in each group
 
The percentage of participants reporting prompted systemic events within 7 days after each vaccination in each group
 
The percentage of participants reporting AEs from Dose 1 through 1 month after Dose 3 in each group
 
	
 
Prompted local reactions (redness, swelling, and pain at the injection site)
 
Prompted systemic events (fever, decreased appetite, drowsiness/increased sleep, and irritability)
 
AEs
 
SAEs
 
NDCMCs
 

Table 2.List of Primary, Secondary,and Estimands

**Objectives**, Endpoints,

Table 2.	List of Primary, Secondary, CCI	Objectives , Endpoints,
	and Estimands	

Primary Safety Objective	Primary Safety Estimands	Primary Safety Endpoints	
	• The percentage of participants reporting AEs from Dose 4 through 1 month after Dose 4 in each group		
	• The percentages of participants reporting SAEs up to 6 months after Dose 4 in each group		
	• The percentages of participants reporting NDCMCs up to 6 months after Dose 4 in each group		

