## 4. ANALYSIS SETS (POPULATIONS FOR ANALYSIS)

Analysis populations are defined for the statistical analysis of safety results in the table below. Data for all participants will be assessed to determine if participants meet the criteria for inclusion in each analysis population prior to unblinding and releasing the database for analysis, and the classifications will be documented per standard operating procedures.

Population	Description
Enrolled	All participants who sign the ICD.
Randomized	All participants who are assigned a randomization number in the IRT system.
Safety	All participants who receive at least 1 dose of the investigational product with safety follow-up after any dose.
	Participants will be grouped according to the vaccine as administered in the safety analysis.
	Safety data after Dose 4 will be summarized for the subset of the safety population who also receive Dose 4 with safety follow-up after Dose 4.

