## 5.1. Hypotheses and Decision Rules

There is no formal hypothesis test and all statistical analyses will be descriptive.

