#### 5.2.1. Analyses for Binary Data

Descriptive statistics for categorical variables (eg, proportions) are the percentage (%), the numerator (n) and the denominator (N) used in the percentage calculation, and the 95% CI where applicable.

The exact 95% CI for binary endpoints for each group will be computed using the F distribution (Clopper-Pearson). The 95% CI for the between-group difference for binary endpoints will be calculated using the Miettinen and Nurminen method.

The 3-tier approach will be used to summarize AEs. For both Tier 1 (if any are identified during the study) and Tier 2 events, a 95% CI for the between-group difference in proportions will be calculated based on the Miettinen and Nurminen method. In addition, for Tier 1 events (if any), the asymptotic p-values will also be presented for the difference in proportions, based on the same test statistic and under the assumption that the test statistic is asymptotically normally distributed. For Tier 3 events, counts and percentages for each vaccine group will be provided.

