#### 6.1.1.1.1. Main Analysis

- Estimand: The percentage of participants reporting prompted local reactions (redness, swelling, and pain at the injection site) within 7 days after each dose (Section 2.1).
- Analysis set: Safety population (Section 4).
- Analysis time point: Within 7 days after each dose.
- Analysis methodology: The between-group difference (20vPnC 13vPnC) and the corresponding 2-sided 95% CI will be calculated using the Miettinen and Nurminen method (Section 5.2.1) for each reaction.
- Intercurrent events and missing data: Missing values will not be imputed.

 Reporting results: Count and percentage of participants with the indicated endpoint and the associated 2-sided 95% CI for each and any local reaction after each dose in each vaccine group will be presented by maximum severity across severity levels. Between-group differences (20vPnC – 13vPnC) in these percentages and their 2-sided 95% CIs will also be provided.

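### Does the SAP leave out a needed between-group comparison by not listing a difference CI for any AE, any SAE and any NDCMC?

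*SAP*

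**What the plan says.** The primary objective is to describe the safety profile of 20vPnC. The estimands in SAP 2.1 are group-wise, for example "The percentage of participants reporting AEs from Dose 1 through 1 month after Dose 3 in each group", and the SAE and NDCMC estimands have the same form. SAP 5.1 adds: "There is no formal hypothesis test and all statistical analyses will be descriptive".

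The reporting commitments in SAP section 6 differ by endpoint:

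- **Prompted local reactions and systemic events (6.1.1.1.1, 6.1.1.2.1).** Each and any event is reported by group with a CI, and the between-group differences "in these percentages and their 2-sided 95% CIs will also be provided".
- **AEs (6.1.1.3.1), in two periods.** The n, N, percentage and CI for "participants reporting any AE, each system organ class, and each preferred term within system organ class will be presented by vaccine group". A difference is then added "for AEs classified as Tier 2 events, the differences in percentages", with CIs, and also for Tier 1 events if any are identified.
- **SAEs and NDCMCs (6.1.1.4.1).** The n, N, percentage and CI for "participants reporting any SAEs/NDCMCs, each system organ class, and each preferred term within system organ class will be presented by vaccine group". No difference is mentioned.

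SAP 5.2.1 gives the general method: "The 95% CI for the between-group difference for binary endpoints will be calculated using the" Miettinen and Nurminen method. It then assigns a difference CI to Tier 1 and Tier 2 events, and counts and percentages to Tier 3.

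Protocol 9.4.1 plans counts, percentages and Clopper-Pearson intervals for SAEs and NDCMCs by vaccine group, also without a difference.

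**The concern.** Protocol 4.2 makes 13vPnC the comparator for the safety assessment, and the study is meant to supply key safety data for licensure. One would expect the broadest safety rows (any AE in each of two periods, any SAE, any NDCMC) to show the randomized comparison. Instead, a single preferred term reported by 1% of one group gets a difference CI, and so does the any-reaction row for prompted events, while these four rows have no such commitment in the legible text. A Tier 2 event is by definition a MedDRA preferred term (SAP 3.1.1.4), so any AE cannot enter through the tier rule.

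SAP 5.2.1 does not clearly close the gap. Its general sentence could cover every binary endpoint, or could only name the method for use where section 6 calls for a difference. Two programmers might build different tables. If the comparison were truly lost, a reader could not see how large an excess of overall AEs, SAEs or NDCMCs on 20vPnC remained compatible with the data. Two separate group intervals do not answer that.

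**Working it through.** **1. The plan's own figures.** The nearest stated numbers are in protocol Table 4, the chance of at least one AE, 1 − (1 − p)^n. For n = 1000 and p = 0.3%, 1 − 0.997^1000 = 95.04%, printed as 95.0%. For n = 500 and p = 0.3% the result is 77.74%, printed as 77.7%. All ten entries reproduce. None depends on whether a difference is displayed.

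**2. Does the planned output estimate what the plan sets out to estimate?**

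| Endpoint | Estimand (SAP 2.1) | Planned output (SAP section 6) | Estimand covered? |
|---|---|---|---|
| Any AE, Dose 1 to 1 month after Dose 3 | % in each group | n, N, %, 95% CI by group | Yes |
| Any AE, Dose 4 to 1 month after Dose 4 | % in each group | n, N, %, 95% CI by group | Yes |
| Any SAE | % in each group | n, N, %, 95% CI by group | Yes |
| Any NDCMC | % in each group | n, N, %, 95% CI by group | Yes |

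No estimand is a difference, and no hypothesis or decision rule uses one.

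**3. Is the comparison lost?** The Miettinen-Nurminen interval for p1 − p2 consists of all D satisfying

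|d − D| / √v(D) ≤ 1.96, where v(D) = [P1(1 − P1)/n1 + P2(1 − P2)/n2] × N/(N − 1),

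with d the observed difference, N = n1 + n2, and P1, P2 the maximum likelihood estimates under P1 − P2 = D. It depends only on x1, n1, x2 and n2. SAP section 6 commits to reporting all four for each of these rows. For the Dose 4 AE row, SAP section 4 fixes the denominator group: "Safety data after Dose 4 will be summarized for the subset of the safety population who also receive Dose 4 with safety follow-up".

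**4. What a derived interval would look like.** Group sizes of about 1000 and 500 come from protocol 4.1.2. The documents give no expected rates, so the rates below are assumptions, with equal observed percentages in both groups:

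| Assumed rate | Counts | 95% CI for the difference (points) |
|---|---|---|
| 1% | 10 vs 5 | −1.39 to 1.02 |
| 2% | 20 vs 10 | −1.78 to 1.42 |
| 5% | 50 vs 25 | −2.56 to 2.22 |
| 20% | 200 vs 100 | −4.4 to 4.2 |
| 50% | 500 vs 250 | −5.36 to 5.36 |

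A hand check at 50% with the simple normal formula: 1.96 × √(0.25 × (1/1000 + 1/500)) = 1.96 × 0.0274 = 5.37 points, in line with the last row. If 10% are assumed missing from the Dose 4 subset (900 vs 450), the 50% row becomes −5.65 to 5.65; if 20% (800 vs 400), −5.99 to 5.99.

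**5. A case chosen to favour the concern.** Assume 50/1000 and 13/500. The Clopper-Pearson intervals, 3.73 to 6.54% and 1.39 to 4.41%, overlap. The difference is 5.0 − 2.6 = 2.4 points, with interval 0.28 to 4.31, which excludes zero. Overlap of the group intervals would therefore mislead. But the interval just given was computed from 50, 1000, 13 and 500 alone, which the planned table would print.

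**6. Do the documents conflict?** Protocol 9.4.1 and SAP 6.1.1.4.1 both give SAE and NDCMC results by group with a CI and no difference. For AEs, both attach differences to Tier 1 and Tier 2 events. The two documents agree.

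**The case for a change.** The strongest case for keeping the point is that a controlled safety study ought to print its headline comparison. Four more rows would use a method already planned, would need no new data, p-value or protocol amendment, and would make the AE, SAE and NDCMC tables consistent with the prompted-event tables. Committing to them before unblinding would also remove any suspicion that comparisons were picked afterwards.

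Part of this stands. The legible text of SAP 6.1.1.3.1 and 6.1.1.4.1 does not promise these four differences, and the general sentence in SAP 5.2.1 does not say whether it reaches them. The rows would be convenient.

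The rest does not make it a fault:

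- The counts for all four rows are committed in advance, so no result can be withheld, and no conclusion depends on a test.
- The different treatment follows the tier scheme: differences go to prespecified events and to relatively common preferred terms. That is a choice, applied alike in both documents.
- SAP 5.2.1 is not silent on scope, because it places Tier 1, Tier 2 and Tier 3 explicitly. If its general sentence does cover all binary endpoints, the four differences are already planned.
- Text next to SAP 6.1.1.3.1 is blacked out and may contain further AE analyses, so absence cannot be shown for the two AE rows. This does not help for SAEs and NDCMCs, since no redaction is visible within 6.1.1.4.1.

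**Conclusion.** The concern does not hold. Followed exactly as written, the plan estimates every primary safety estimand, with n, N, percentage and a 95% CI in each group, and the protocol and SAP agree on this. The effect on any estimate, sample size, error rate or decision is nil. What is missing from the legible text is a printed difference for four rows, and each can be computed exactly from counts the plan commits to report. Its half-width would be about 1.2 points at an assumed 1% and about 5.4 points at an assumed 50%, given 1000 versus 500 participants and equal observed percentages; those rates are assumptions, because the documents give none.

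The conclusion rests on two stated features of the plan: the objective is descriptive with group-wise estimands, and n and N are reported for each overall row. If the study had a comparative estimand or a decision rule for overall AEs, SAEs or NDCMCs, the same omission would matter.

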# 6.2. Secondary Endpoints

Not applicable.

CCI
PFIZER CONFIDENTIAL
Page 18

#### 6.4. Baseline and Other Summaries and Analyses

#### 6.4.1. Baseline Summaries

CI

#### 6.4.1.1. Demographic Characteristics

Demographic characteristics, including age at each dose, sex, race, ethnicity, racial designation, country/region, and gestational age, will be summarized for the safety population for each vaccine group and overall. Similar summaries will be done for the randomized population.

#### 6.4.1.2. Medical History

Each reported medical history term will be mapped to a system organ class and preferred term according to MedDRA. The number and percentage of participants with an assigned vaccine having at least 1 diagnosis, overall and at each system organ class and preferred term level, will be summarized by vaccine group for the safety population.

#### 6.4.2. Study Conduct and Participant Disposition

#### 6.4.2.1. Participant Disposition

The number and percentage of randomized participants will be included in the participant disposition summary. In addition, the numbers and percentages of participants who received each vaccination (Dose 1, 2, 3, or 4), who completed the follow-up visits (1 month after Dose 3, 1 month after Dose 4), who completed the 6-month telephone contact, who completed all visits, who withdrew before the visit 1 month after Dose 3, who withdrew after the visit 1 month after Dose 4 but before the visit 1 month after Dose 4 but before the visit 1 month after Dose 4, and who withdrew after the visit 1 month after Dose 4, along with the reasons for withdrawal, will be tabulated by vaccine group (according to randomized group assignment). The reasons for withdrawal will be those as specified in the database.

Randomized participants excluded from the safety analysis population will also be summarized separately, along with the reasons for exclusion, by vaccine group.

## 6.4.3. Study Vaccination Exposure

## 6.4.3.1. Vaccination Timing and Administration

For each dose, the number and percentage of participants randomized and receiving each investigational product (20vPnC or 13vPnC), as well as the corresponding concomitant vaccines, will be tabulated for each vaccine group and overall for all randomized participants. The denominator for the percentage calculations is the total number of randomized participants in the given vaccine group or overall. A listing of participants who received a vaccine other than what they were randomized to receive will be produced, if any such incorrect dosing occurs.

A listing of participants showing the randomized vaccine and the vaccine actually received (20vPnC or 13vPnC) at each dose will be presented.

# 6.4.4. Prior/Concomitant Vaccination and Concomitant Medications Used to Treat SAEs and NDCMCs

Each prior/concomitant vaccine will be summarized according to the ATC fourth-level classification. The prior/concomitant vaccine received before Dose 1 will be listed. The number and percentage of randomized participants receiving each vaccine after Dose 1 will be tabulated according to vaccine group for all randomized participants. Summarization will be done separately for concomitant vaccines received:

- with Dose 1, Dose 2, Dose 3, or Dose 4, separately
- between Dose 1 and 1 month after Dose 3
- between 1 month after Dose 3 and Dose 4
- between Dose 4 and 1 month after Dose 4

Concomitant medications used to treat SAEs and NDCMCs will be summarized from Dose 1 through the 6-month follow-up telephone contact. The safety population will be used.

## 6.5. Safety Summaries and Analyses

Summaries and analyses of the safety measures local reactions, systemic events, AEs, SAEs, and NDCMCs are described under Primary Safety Endpoints (see Section 6.1.1).

## 7. INTERIM ANALYSES

No interim analysis is planned in this study. Statistical analyses will be carried out when the final data for the specified analyses are available.

ſ	2	ſ	2	
L	ر	L	ر	

PFIZER CONFIDENTIAL	,
Page 20	

#### 7.1. Introduction

Not applicable.

#### 7.2. Analysis Timings

Statistical analyses are planned to be carried out when the final data for the specified analyses are available:

- Primary Analysis 1: Safety data through the visit occurring 1 month after Dose 4 from all participants may be analyzed by the study team when available (at which time the study team will be unblinded).
- Final Analysis: Safety data from 1 month after Dose 4 through the visit occurring 6 months after Dose 4 from all participants.

The study team will remain blinded up to Primary Analysis 1, if it is undertaken; otherwise, they will be blinded until the last participant completes the study. The investigator site staff will remain blinded to participant vaccine group until the last participant completes the final visit telephone call.

# 9. APPENDICES

# **Appendix 1. List of Abbreviations**

Abbreviation	Term
13vPnC	13-valent pneumococcal conjugate vaccine
20vPnC	20-valent pneumococcal conjugate vaccine
AE	adverse event
ATC	Anatomic Therapeutic Chemical
CI	confidence interval
COVID-19	coronavirus disease 2019
CRF	case report form
e-diary	electronic diary
CCI	
ICD	informed consent document
IRT	interactive response technology
MedDRA	Medical Dictionary for Regulatory Activities
N/A	not applicable
NDCMC	newly diagnosed chronic medical condition
SAE	serious adverse event
SAP	statistical analysis plan
WHO	World Health Organization
